10.7.5 Physical Examination

Complete Physical Examination will be assessed at screening. Partial Physical Examination will be assessed at Day 1, Day 2 to Day 28 or discharge (if discharge happens earlier). Complete Physical examination will include general appearance, skin, head, neck, ENT, heart, lungs, abdomen, extremities, neurological, musculoskeletal, and lymph nodes. Partial Physical examination will include general appearance, ENT, heart and lungs nodes.

Physical Examination findings will be summarized by frequencies and percentages using the SAF population and treatment group.

Listing will be provided by subject for the Physical Examination.

10.7.6 Chest X ray

Chest X ray will be assessed at screening, Baseline, Day 4, Day 7, Day 10, Day 14 and Day 28/EOS.

The chest-X ray analysis has been described in the secondary endpoint section point number 9;

Listing will be provided by subject for the Chest-X ray.

10.7.7 Pregnancy Test

Listing will be provided for female subjects for the serum Pregnancy Test at each time point

10.7.8 IMP Administration

Listing will be provided for the IMP administration along with treatment compliance for each patient.

10.7.9 COVID-19 associated symptom severity assessment

COVID-19 associated symptom severity will be assessed at screening. Day 1, Day 2 to Day 28 or discharge (if discharge happens earlier).

COVID-19 associated symptom severity assessment parameters will be summarized by frequencies and percentages using the SAF population by study day and treatment group.

Listing will be provided for the COVID-19 associated symptom severity assessment.

Statistical Analysis Plan
Sponsor: [name], Inc

Study Number: NV-05-983-2020

Version: 2.0 Date: 06JAN2021

10.7.10 Hospitalization

Listing of patients who require oxygen supplementation, ICU admission, Oxygen by HFNC or NIV and Invasive Mechanical Ventilation will be listed.

10.7.11 Subgroup Analysis:

Subgroup analysis will be performed for the “Time to resolution of hypoxia” by considering the severity category (moderate vs severe categories) as a subgroup using ITT population as an observed case analysis.

Subgroup analysis will be performed for the “Time to resolution of hypoxia” by considering the race category (White/ Caucasian vs Non-White / Non-Caucasian) as a subgroup using ITT population as an observed case analysis.

Subgroup analysis will be performed for the “Time to resolution of hypoxia” by considering the age category (Age group <50 years, Age group ≥50 years) as a subgroup using ITT population as an observed case analysis.

Subgroup analysis will be performed for the “Time to resolution of hypoxia” by considering the gender category as a subgroup using ITT population as an observed case analysis.

11 Deviation from the Study Protocol

Not applicable

12 Database Lock and Unblinding

There will be two database lock for this study. One for stage I (Primary) and another one for Stage II (Secondary) analysis. The SAP will be finalized prior to primary database lock. After the data cleaning process is finalized according to the data management plan (DMP) and the assignment of patients to the analysis populations is agreed and signed by the Sponsor, the study database will be locked for primary and secondary separately.

13 References

1. Lachin J. M. (1999). *Worst-Rank Score Analysis with Informatively Missing Observations in Clinical Trials. Controlled Clinical Trials. 20:408–422.*

	Statistical Analysis Plan Sponsor: [name], Inc	
	Study Number: NV-05-983-2020	Version: 2.0 Date: 06JAN2021

14 Appendices

Appendix I: Interim Analysis Plan

Statistical Analysis Plan
Sponsor: [name], Inc

Study Number: NV-05-983-2020

Version: 2.0 Date: 06JAN2021

Appendix I: Interim Analysis Plan

A single unblinded interim analysis of the primary efficacy endpoint, that is, time to resolution of hypoxia, will be conducted. Resolution of hypoxia is defined as described in Section 10.6.1. This endpoint will be considered to have been met when the patient had attained a score of 4 or lower on the 10-point ordinal scale of clinical status used by the WHO in the SOLIDARITY trial, and either maintained the score of 4 or lower for five consecutive assessments over 5 days or was discharged after reaching the score of 4 or lower. In addition, the patient must also survive and not be readmitted to hospital due to COVID-19 related complications through Day 28 to be considered meeting the endpoint. To be performed when data for time to resolution of hypoxia become available for either the first 390 randomized subjects (50% of the target enrollment) or subjects enrolled by the end of year 2020, whichever is earlier, interim analysis will be conducted for three purposes: 1) Possible early stopping for demonstrated efficacy of the study treatment, 2) Possible early stopping for futility (lack of efficacy), and 3) Sample size reassessment. After reviewing the analysis, the DMC will make a recommendation concerning continuation of the study as planned, termination, or continuation with a larger sample size.

The interim analysis for efficacy will be performed like the primary efficacy analysis detailed in Section [10.6.1](#) of the Statistical Analysis Plan for the final analysis. Time to resolution of hypoxia will be compared between the treatment groups using the Cox proportional hazard model with age, gender, and baseline score on the 10-point ordinal scale of clinical status as covariates. A Lan-DeMets alpha spending function approach will be adopted in order to maintain the overall Type-I error or alpha at the desired two-sided 0.05 level (Lan & DeMets, 1983). The boundary for possible early stopping for demonstrated efficacy will be determined using a Type I error rate of 0.005 (one-sided); that is, the null hypothesis of zero treatment effect will be rejected if the observed effect is in the direction of treatment benefit and it is significant with one-sided $p < 0.005$. If the trial is not stopped after the interim analysis, the final primary efficacy analysis conducted upon study completion will be based on an adjusted Type I error rate of two-sided 0.04521 (i.e., the result will be considered statistically significant for a Z-statistic ≥ 2.0027).

Assuming the Z-statistic does not reach the boundary for early stopping for demonstrated efficacy, an analysis will be conducted for possible early stopping for futility. A DMC recommendation of early stopping for futility will be based on two factors. The first factor is the conditional power, i.e., the probability of finding a significant beneficial treatment effect with adjusted Type I error rate of two-sided 0.04521 at the end of the study, given the current data and appropriate assumptions about the true treatment effect. The second factor is the estimated effect size from the interim analysis. The DMC may recommend the study be stopped for reasons of futility if either 1) the conditional power is very low (for example, 20% or lower), assuming a hazard ratio equal to the estimated hazard ratio from the current data, or 2) the upper limit of a 95% confidence interval for the difference in median time to resolution of hypoxia is < 1 day. The conditional

Statistical Analysis Plan
Sponsor: [name], Inc

Study Number: NV-05-983-2020

Version: 2.0 Date: 06JAN2021

power will be calculated as in Lachin (2005) and Chen, DeMets, & Lan (2004). Median times to resolution of hypoxia will be estimated by the Kaplan-Meier method.

If the interim analysis results do not suggest early stopping for efficacy or futility, the DMC will consider whether to recommend an increase in sample size, following the method given by Chen, DeMets, & Lan (2004). Conditional power will be calculated under the assumption that the true underlying hazard ratio is the same as the estimate from the current data. If this conditional power is less than 80%, the increase in sample size necessary to make the conditional power 70%, 75%, or 80% will be calculated. If the conditional power with the currently planned sample size is $\geq 50\%$ and the sample size increment required for the desired power is less than approximately 1.5 times the original sample size, increasing sample size by this method will not affect the Type I error rate. In addition, simulations suggest the Type I error in this analysis will not be inflated for conditional power $\geq 20\%$ and $< 50\%$, as long as there is a stopping rule for very low conditional power (Lan & Trost, 1997). If the increase in sample size required to achieve a desired power is not feasible, a smaller increase may be made.

Two key secondary endpoints will also be analyzed in the interim analysis for considering by the DMC in their deliberations. These two endpoints are time to discharge from hospital and time to improvement from baseline of at least 2 points on the 10-point clinical status scale. Cox models and Kaplan-Meier analysis will be employed, as for the primary endpoint. Missing values will not be imputed.

Mortality and disease progression endpoints will be analyzed in the interim analysis. These analyses will be exploratory and will be based on the observed data only. The mortality endpoints will include patients dying from any cause and patients dying from a COVID-19 associated complication. Between-treatment comparisons will be performed for these mortality endpoints, as both binary and as time to event outcomes. For disease progression, patients requiring, until the earlier of Day 28 or discharge from hospital, management in intensive care unit, high flow nasal oxygen / non-invasive mechanical ventilation, and invasive mechanical ventilation will be separately tabulated. Time from randomization to each of these disease progression events will be compared between treatments. In addition, the duration of requiring (as measured by the number of days) management in intensive care unit, non-invasive mechanical ventilation, and invasive mechanical ventilation will be compared separately. Covariate-adjusted analyses will be performed if needed.

References:

Chen, Y. H., DeMets, D. L., & Lan, K. K. G. (2004). Increasing the sample size when the unblinded interim result is promising. Stat Med. 23(7): 1023-38.

Lachin J. M. (2005). A review of methods for futility stopping based on conditional power. Stat Med. 24: 2747-2764.

Statistical Analysis Plan
Sponsor: [name], Inc

Study Number: NV-05-983-2020

Version: 2.0 Date: 06JAN2021

Lan K. K. G., DeMets D. L. (1983). Discrete sequential boundaries for clinical trials. Biometrika. 70: 659–663.

Lan, K. K. G., Trost D. C. (1997). Estimation of parameters and sample size re-estimation. Proceedings of the American Statistical Association, Biopharmaceutical Section: 48-51.

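### The final boundary of Z ≥ 2.0027 holds benefit-side error at 0.025 only for an interim at 50% information; the SAP allows an earlier interim and does not say the boundary will be recomputed (small effect)

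*SAP*

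**What the plan says.** Everything relevant is in SAP Appendix I (Interim Analysis Plan).

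- **Timing.** The one unblinded interim takes place when primary endpoint data are available for "either the first 390 randomized subjects (50% of the target enrollment) or subjects enrolled by the end of year 2020, whichever is earlier".
- **Error target and method.** "A Lan-DeMets alpha spending function approach will be adopted" in order to "maintain the overall Type-I error or alpha at the desired two-sided 0.05 level". No spending function is named.
- **Interim efficacy rule.** The null is rejected if "the observed effect is in the direction of treatment benefit and it is significant with one-sided" p below 0.005. There is no interim boundary for harm on this test.
- **Final rule.** The final analysis uses "an adjusted Type I error rate of two-sided 0.04521 (i.e., the result will be considered statistically significant for a Z-statistic ≥ 2.0027").

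The same 0.04521 enters the conditional power used for futility, and the final criterion underlies the conditional power used for sample-size reassessment. Neither Appendix I nor SAP sections 9.6 and 9.7 says that 0.005 or 2.0027 will be revisited at the information fraction actually observed. Enrolment at the end of 2020 is not reported.

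**The concern.** Under a Lan-DeMets approach the boundary at each look follows from the information observed at that look. Appendix I names the approach and then fixes the final number in advance, while its calendar clause leaves the interim fraction open.

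The direction is clear once the interim spend is held at 0.005. An earlier look makes the interim and final statistics less correlated, so the two chances of a false claim overlap less. The final boundary then has to rise to hold the same cumulative error. At stake is the pass/fail line of the primary analysis: a final Z between 2.0027 and the recomputed value would be declared positive without having crossed a boundary that holds one-sided 0.025.

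**Working it through.** **Inputs.** From SAP Appendix I: one-sided interim alpha 0.005, i.e. Z₁ boundary 2.5758; final critical value c = 2.0027; overall two-sided 0.05, i.e. 0.025 on the benefit side. From SAP section 9.6: 780 patients randomized and 631 planned events. *Assumption:* information is proportional to patients, so t = n/780. The true measure for a Cox test is events; half of 631 is about 316.

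**Model.** Under the null, Z₁ and Z₂ are standard bivariate normal with correlation √t. The benefit-side error is

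α₊(t, c) = 0.005 + P(Z₁ < 2.5758, Z₂ ≥ c),

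and the required c solves P(Z₁ < 2.5758, Z₂ ≥ c) = 0.025 − 0.005 = 0.020.

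**Reproducing the SAP figure.** At t = 390/780 = 0.50 (correlation 0.7071) the solution is c = 2.0027, and 2 × P(Z ≥ 2.0027) = 0.04521. Both printed values match. Solving backwards, 2.0027 corresponds to t = 0.5003, which is 0.50 up to rounding.

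**Earlier looks, 0.005 kept at the interim.** The last two columns keep c at 2.0027.

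| Patients at interim | t | Required final Z | Nominal two-sided p | Benefit-side error at 2.0027 | Total error at 2.0027 |
|---|---|---|---|---|---|
| 390 | 0.500 | 2.0027 | 0.0452 | 0.0250 | 0.0476 |
| 350 | 0.449 | 2.0083 | 0.0446 | 0.0253 | 0.0479 |
| 300 | 0.385 | 2.0150 | 0.0439 | 0.0256 | 0.0482 |
| 200 | 0.256 | 2.0277 | 0.0426 | 0.0263 | 0.0489 |
| 100 | 0.128 | 2.0392 | 0.0414 | 0.0269 | 0.0495 |

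Total error follows the rule as written: benefit-only rejection at the interim and a two-sided final test. It adds P(Z₁ < 2.5758, Z₂ ≤ −2.0027) ≈ 0.0226 to the benefit-side error. At 300 patients, for example, 0.0256 + 0.0226 = 0.0482.

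**Ceiling.** As t approaches 0 the two statistics become independent and the benefit-side error tends to 0.005 + 0.995 × 0.022605 = 0.0275.

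**Width of the affected band.** It is 2.0150 − 2.0027 = 0.012 in Z at 300 patients, 0.025 at 200 and 0.037 at 100 (2.0392 − 2.0027 = 0.0365).

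**The case against.** The strongest reply is that the stated promise is kept. Appendix I undertakes to hold a two-sided 0.05, and under its own rule total error is between 0.0476 and 0.0495 over the range tabulated. That stands. A reader might double the benefit-side figures and infer an overall two-sided error of 0.051 to 0.054. Doubling presumes a mirror-image harm boundary at the interim, which the SAP does not have, so those are not this plan's error rates. What the reply does not explain is the number itself. Counted that way, 2.0027 would give 0.0476 at 50%, not 0.05; it is exact only for 0.025 on the benefit side, which is also the error that supports an efficacy claim. The 0.025 criterion is inferred from that match; Appendix I does not state it.

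Four further points:

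- *The final boundary need not rise.* True if a spending function also lowered the interim alpha at an earlier look. A power-family function through 0.005 at t = 0.50 would spend 0.0030 at t = 0.40 and give a final value of 1.9877. The SAP names no function and fixes 0.005, so this cannot be credited.
- *The earlier trigger may never have applied.* This stands. A reader might infer from the SAP date of 06JAN2021 that the calendar limb governed. The date belongs to version 2.0, not necessarily to the figure, and the limb that governs depends on enrolment, which is not reported. The interim also waits for endpoint data that run to Day 28.
- *Patients are not events.* This stands. Fewer than 390 patients does not by itself mean less than 50% information; that depends on the events at each look.
- *Futility stopping offsets the excess.* The rule is advisory, so it cannot be relied on for error control.

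**Conclusion.** The arithmetic behind 2.0027 is correct for a look at 50% information. What is missing is a rule for the case that Appendix I itself allows, a look at less than 50%. There, with 0.005 held at the interim, the fixed boundary lets the benefit-side error rise from 0.0250 to 0.0253–0.0269 for 350 down to 100 patients, and never above about 0.0275.

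This is a real but minor defect. It changes the conclusion only if the final Z falls in a band about 0.01 to 0.04 wide just above 2.0027. The documents do not support saying that the two-sided 0.05 level is breached, or that an error has occurred. The sizes assume information proportional to patients, a final size of 780 and no credit for futility stopping. I have not quantified the effect on conditional power.

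**What to change.** In SAP Appendix I, replace the fixed final threshold with a rule: one-sided 0.005 is spent at the interim, and the final critical value is computed from the observed information fraction (primary events at the interim divided by planned primary events at the final analysis) so that cumulative one-sided alpha is 0.025. Keep 2.0027 (two-sided 0.04521) as the worked example for 50%. Use the recomputed value wherever 0.04521 now enters conditional power and sample-size reassessment. Make the change before the final analysis, so that it cannot appear to be driven by the result.

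The cost is one paragraph and one recalculation. If the interim was early, the final threshold becomes slightly stricter, for example 2.015 instead of 2.0027 at 300 patients. If it fell at 50% of events, the rule returns the value already printed.
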